6.3 Randomization

Approximately 490 subjects (245 per arm) who meet eligibility criteria will be stratified by age at Screening Visit (<18 versus \geq 18 years of age), sex (male versus female), and percent predicted FEV₁ severity determined during the Screening Period (<70 versus \geq 70), and then randomized (1:1) to either TEZ/IVA or placebo. An interactive web response system (IWRS) will be used for randomization following a list of randomization codes generated by a designated vendor [REDACTED].

6.4 Blinding and Unblinding

This is a double-blind study.

6.4.1 Blinding

The subjects and all site personnel, including the investigator, the site monitor, and the study team, will be blinded with the exception of the following:

- Any site personnel for whom this information is important to ensure the safety of the subject in the event of a life-threatening medical emergency. Such unblinding events will be fully documented (see below).
- Any site personnel for whom this information is important to ensure the safety of the subject and her fetus in the event of a pregnancy. Such unblinding events will be fully documented (see below).
- Vertex Global Patient Safety (GPS) and Regulatory Affairs personnel to satisfy SAE processing and reporting regulations
- Unblinded statistician preparing the final (production) randomization list who is not part of the study team
- Vertex Clinical Operations IWRS management
- Vertex Clinical Supply Chain
- IDMC
- Vendor preparing the unblinded analysis for the IDMC
- Vendor analyzing PK samples
- Vertex or vendor conducting the population PK analysis
- Vertex Medical Monitor may, for matters relating to safety concerns, unblind individual subjects at any time. Such unblinding events will be fully documented (see below).

Vertex Drug Metabolism and Pharmacokinetics laboratory personnel will not be involved in the conduct of the study and will be unblinded to the bioanalysis results and will remain blinded to subject number and treatment assignment.

Spirometry Data Blinding

Despite treatment blinding, knowledge of the spirometry results has the potential to suggest whether a subject has been administered active study drug or placebo. Therefore, during the conduct of the study, the Vertex study team will have no access to the post-dose spirometry data. The vendor for central reading of the spirometry data will only send the blinded spirometry files (blinded treatment group, with real values for screening and baseline, but with dummy values for all the spirometry assessment after baseline) to Vertex to be used for developing the statistical programs. Furthermore, subjects and their caregiver should not be informed of their study-related spirometry results during the Treatment Period regardless of whether the subject has prematurely discontinued treatment

Sweat Chloride Data Blinding

Despite treatment blinding, knowledge of the sweat chloride data has the potential to suggest whether a subject has been administered active study drug or placebo. Therefore, during the conduct of the study, the Vertex study team will have no access to the post-dose sweat chloride data; dummy data will be used to develop statistical programs. During the process of locking the clinical database, after all study visits have been completed, access to treatment-blinded sweat chloride data will be provided to a small group of individuals (a biostatistician, a statistical programmer, a validation statistical programmer, and a clinical reviewer) who are part of the Vertex study team. This small group will review the sweat chloride data to ensure there are no significant data issues and will use the blinded data set to refine the statistical programs.

6.4.2 Unblinding

At the initiation of the study, the study site will be instructed on the method for breaking the blind. The unblinding method will be either a manual or electronic process.

Unblinding of the individual subject's treatment by the investigator will be limited to medical emergencies or urgent clinical situations in which knowledge of the subject's study treatment is necessary for clinical management. In such cases, investigators should use their best judgment as to whether to unblind without first attempting to contact the medical monitor to discuss and agree to the need for unblinding. If investigators deem that it is not necessary to unblind immediately, they will first attempt to contact the medical monitor to discuss and agree to the need for unblinding. If investigators have tried but are unable to reach the medical monitor, they should use their best judgment, based on the nature and urgency of the clinical situation, and may proceed with unblinding.

Contact information for the medical monitor (or appropriate backup) will be provided in a separate document.

In addition, the Vertex Medical Information Call Center [REDACTED] will answer calls 24 hours a day, 7 days a week, 365 days of the year, and will triage these calls to the study medical monitor or appropriate backup.

If a subject's treatment assignment has been unblinded for a medical emergency or urgent clinical situation, the medical monitor should be notified within 24 hours of the unblinding event. The reason and the date of the unblinding will be documented clearly in the subject's study file. Information about the treatment assignment obtained from the unblinding will be maintained in a secure location with controlled access and will not be shared with sponsor (Vertex), contract research organization (CRO), or any site personnel (other than the physician treating the subject). In addition, the investigator will consider whether the clinical event that prompted unblinding will be considered an SAE, according to the regulatory definitions or criteria for SAEs, and if so, submit an SAE report to Vertex GPS or designee, per Protocol Section 13.1.2.

Vertex GPS or designee will also unblind any SAE reports in compliance with regulatory reporting requirements. In addition, the Vertex medical monitor may, for matters relating to safety concerns, unblind individual subjects at any time.

7 ANALYSIS SETS

The following analysis sets are defined: All Subjects Set, Randomized Set, Full Analysis Set (FAS), and Safety Set.

The **All Subjects Set** is defined as all subjects who have been randomized or have received at least 1 dose of study medication. This analysis set will be used in subject listings and the disposition summary table, unless otherwise specified.

The **Randomized Set** is defined as all subjects who have been randomized.

The **Full Analysis Set (FAS)** is defined as all randomized subjects who carry the intended CFTR allele mutation and have received at least 1 dose of study drug.

The **Safety Set** is defined as all subjects who received at least 1 dose of study drug.

8 STATISTICAL ANALYSIS

8.1 General Considerations

All individual subject data in the All Subject Set will be presented in data listings. The Schedule of Assessments is provided in Section 11.1. The precision standards are provided in Section 11.6.

Continuous variables will be summarized using the following descriptive summary statistics: the number of subjects (n), mean, standard deviation (SD), median, minimum value (min), and maximum value (max).

Categorical variables will be summarized using counts and percentages.

Baseline Value, unless otherwise specified, is defined as the most recent non-missing measurement (scheduled or unscheduled) collected prior to or on the first dose of study drug. For ECGs, the baseline will be defined as the average of the 3 pre-treatment measurements (triplicate) on Day 1. For sweat chloride, the baseline value will be the mean of last assessment values on the left and the right arm prior to the first dose of the study drug.

Change (Absolute Change) from baseline will be calculated as Post-baseline value – Baseline value.

Relative change from baseline will be calculated and expressed in percentage as $100 \times (\text{Post-baseline value} - \text{Baseline value}) / \text{Baseline value}$.

Treatment Emergent (TE) Period will include the time from the first dose of study drug to the Safety Follow-up Visit, or to 28 days after the last dose of the study drug for subjects who do not have a Safety Follow-up Visit, or to the last participation date in the study (i.e., the day right before the first study dose in the extension study for subjects who enrolled into the extension study), whichever occurs first. The TE period will be used for safety analyses unless otherwise specified.

Unscheduled Visits: Unscheduled visit measurements will be included in the following:

1. derivations of measurements at scheduled visits per specified visit windowing rules below;
2. derivations of baseline/last on-treatment measurements;
3. derivations of the maximum/minimum on-treatment values and maximum/minimum changes from baseline values for safety analyses;
4. data listings where appropriate.

Visit Windowing Rules: Section 11.2 defines the windows for protocol-defined visits. The windows will be applied using the following rules for both scheduled and unscheduled visits:

1. If no measurement is available within a visit window, the assessment will be considered missing for the visit;
2. If there is more than one measurement available within the same visit window, use the following rules:
 - For all efficacy parameters, if there are multiple measurements within a visit window, the record at the scheduled visit will be used. Otherwise,
 - The record closest to the target day will be used;
 - If there are multiple records with the same distance to the target day, the latest record will be used.
 - Assessments at early treatment termination (ETT) visit will follow the windowing rules for regular visits up to Week 24.
 - Assessments at safety follow-up (SFU) visit will follow the windowing rules for regular visits if they fall within the upper boundary of the window for

Week 24, or remain as SFU if they go beyond the upper boundary of the window for Week 24.

- For all safety parameters, if there are multiple measurements within a visit window, then 1) the record closest to the target day will be used; 2) if there are multiple records within the same distance from the target day, the latest record will be used; or 3) SFU visit will not be windowed; instead, it will be used according to the nominal visit in relevant analyses.

Note, spirometry assessments, BMI, weight, and height will be used for both efficacy and safety purposes. Their measurements will follow the visit windowing rules for efficacy parameters.

Incomplete/Missing data will not be imputed, unless otherwise specified.

Outliers: No formal statistical analyses will be performed to detect or remedy the presence of statistical outliers, unless otherwise specified.

8.2 Background Characteristics

8.2.1 Subject Disposition

In the summary table of subject disposition, the number of subjects in the following categories will be presented by treatment and overall:

- All Subjects Set (randomized or dosed)
- Randomized Set
- Full Analysis Set (FAS)
- Safety Set

The number and percentage of subjects in each of the following disposition categories will be presented by treatment and overall based on the Safety Set:

- Completed treatment regimen
- Prematurely discontinued the treatment (any tablet) and the reason for discontinuations
- Completed study
- Prematurely discontinued the study and the reasons for discontinuations
- Rollover to extension

A listing will be provided for subjects who discontinued treatment or who discontinued from the study, along with reasons for discontinuations.

The number and percentage of randomized subjects will be summarized by stratification factor, and by country and by site, using the number of subjects being randomized to each treatment group as the denominator. A randomization listing will be provided with subjects ordered by randomization date.

8.2.2 Demographics and Baseline Characteristics

The following demographic data will be summarized by treatment and overall based on the FAS:

- Age at Screening
- Sex
- Ethnicity (Hispanic or Latino, not Hispanic or Latino, not collected per local regulations)
- Race (White, Black or African American, Asian, American Indian or Alaska Native, Native Hawaiian or Other Pacific Islander, Other)
- Geographic region (North America, Europe)

The following baseline characteristics will be summarized:

- Weight (kg)
- Height (cm)
- BMI (kg/m²)
- Weight z-score (subjects <20 years old at screening)
- Height z-score (subjects <20 years old at screening)
- BMI z-score (subjects <20 years old at screening)

Stratification categories (in addition to sex) will also be summarized:

- Age groups at screening (< 18, ≥18 years)
- Percent predicted FEV₁ at screening (<70, ≥70)

Disease characteristics at baseline will include the following:

- Percent predicted FEV₁ categories(<40, ≥40- <70, ≥70-≤90, >90)
- Percent predicted FEV₁
- Sweat chloride
- CFQ-R Respiratory Symptoms domain
- FEV₁ (L)
- FVC (L)
- Percent predicted FVC
- FEF_{25-75%} (L/sec)
- Percent predicted FEF_{25-75%}
- FEV₁/FVC

- Use of dornase alfa
- Use of inhaled antibiotic
- Use of azithromycin
- Use of bronchodilator
- Use of inhaled bronchodilator (short-acting only, [short-acting and long-acting] or long-acting only)
- Use of inhaled hypertonic saline
- Use of inhaled corticosteroids
- Colonization of *Pseudomonas aeruginosa* (Positive, Negative)

In addition, data listings will also be provided for:

- Informed consent;
- Inclusion/Exclusion criteria violation (for subjects with any such violations);

8.2.3 Medical History

Medical history will be coded by using the Medical Dictionary for Regulatory Activities (MedDRA). For the FAS, medical history will be summarized descriptively by system organ class and preferred term. The corresponding data listing will also be provided.

In addition, the number of subjects reported to have had positive cultures for respiratory pathogens in the 2 years prior to screening (i.e., answered yes on the respiratory microbiology form) will be summarized by test and subcategories within the test. The corresponding data listing will be provided. Hospitalization and clinic visit history in the past year will be listed.

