6.2 Sample Size and Power

The study is powered for both the primary endpoint (change from baseline in ppFEV₁) and a secondary endpoint of clinical interest (relative risk of pulmonary exacerbations).

The primary efficacy endpoint is the absolute change from baseline in percent predicted FEV₁ through Week 24.

The null hypothesis to be tested is that the mean absolute change from baseline in percent predicted FEV₁ through Week 24 is the same for TEZ/IVA and placebo. Assuming a common standard deviation (SD) of 8% in each arm, a sample size of 220 subjects in each treatment group will have at least 90% power to detect a treatment difference of 2.5% in percent predicted FEV₁ between treatment groups, using a 2-sided significance level of 0.05. If the above null hypothesis is rejected, the efficacy of TEZ/IVA will be considered established.

Power for pulmonary exacerbation:

Assuming the pulmonary exacerbation rate for placebo is 0.5 events in 24 weeks, with 220 subjects in each treatment group, the power to detect a 40% reduction in the pulmonary exacerbation rate in the active arm versus the placebo arm is about 92%. The power to detect a 33% reduction in the pulmonary exacerbation rate is about 78%.

This power calculation is based on an R simulation with 10,000 replications. To adjust for a 10% dropout, a total sample size of 490 subjects is needed.

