8.3.2.2 Analysis of Secondary Efficacy Endpoints

8.3.2.2.1 Analysis of Key Secondary Efficacy Endpoints

Relative change from baseline in ppFEV₁ through Week 24

Analysis for the relative change from baseline in ppFEV₁ through Week 24 will be similar to that for the primary analysis. The LS Mean (SE) of the overall treatment difference between TEZ/IVA and placebo in the relative change from baseline in percent predicted FEV₁ from Day 15 through Week 24 will be presented along with the 95% confidence interval and a 2-sided *P* value.

The LS Mean (SE) of within-treatment group relative change from baseline at each post-baseline visit along with the corresponding 95% CI and p-value will be estimated from the same MMRM model. The LS Mean (SE) of the treatment difference between TEZ/IVA and placebo at each post-baseline visit will be provided along with the corresponding 95% CI and p-value. The LS means (with 95% CI) at each post-baseline visit will also be plotted by treatment group. Summary statistics of raw values and absolute change from baseline in ppFEV₁ at each visit will be presented. The cumulative distribution of the average relative change from study baseline in ppFEV₁ through week 24 will be plotted by treatment group.

Number of pulmonary exacerbations through Week 24

A negative binomial generalized linear model will be used to compare the rates of pulmonary exacerbations over the 24-week treatment period for the two treatment groups. The estimated rate ratio and the associated 95% CI and p-value will be provided. In this model, the dependent variable will be the number of pulmonary exacerbations through Week 24, (including both on treatment events and events after treatment discontinuation). Treatment, sex, age group at screening (<18 vs. ≥ 18 years old), and baseline percent predicted FEV₁ will be included as covariates. The log of time spent in the study will be treated as the offset in this model. A log link function will be used in this model. If the model does not converge, the negative binomial regression model will be replaced with a Poisson regression model with the same covariates, offset variable, and link function.

Absolute change in BMI from baseline at Week 24

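### The exacerbation-rate model leaves out past-year hospitalization history, which the SAP plans only to list, so precision may be lost on a key secondary endpoint

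*SAP*

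**What the plan says.** SAP 8.3.2.2.1 compares exacerbation rates with a negative binomial model, log link and log time in study as offset. The covariate list begins "Treatment, sex, age group at screening" and ends with continuous baseline ppFEV1. A Poisson model is the fallback if the negative binomial model does not converge. Protocol 12.3.3.2 describes a similar model with ppFEV1 severity at screening in place of the continuous value. Neither has a term for hospitalization or exacerbation history.

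SAP 8.2.3 says: "Hospitalization and clinic visit history in the past year will be listed". The history is not among the baseline characteristics summarized in SAP 8.2.2.

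The endpoint is step 3 of the hierarchy in SAP 8.3.2.2.2, ahead of BMI (step 4) and the CFQ-R respiratory domain (step 5). SAP 6.2 says the study is powered for exacerbations as well as for the primary endpoint. Its planning basis is: "Assuming the pulmonary exacerbation rate for placebo is 0.5 events in 24 weeks, with 220 subjects in each treatment group".

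**The concern.** A subject's past-year hospitalizations plausibly indicate how likely that subject is to exacerbate again. The protocol itself links the two: Section 8.2.4 says exacerbations may require hospitalization, and Section 11.6.12.1 counts those that do. Sex, age group and ppFEV1 describe demographics and lung function, not event history.

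In a negative binomial model, differences between subjects that the covariates do not explain go into the dispersion term and widen the confidence interval for the rate ratio. A prognostic covariate would take up part of that variation. With a log link, adding a balanced baseline covariate leaves the rate ratio being estimated unchanged, so any gain does not come at the price of a different estimand.

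Step 3 also gates steps 4 and 5, so a narrow miss on exacerbations would end formal claims on BMI and CFQ-R too. And because the history is only listed, a chance imbalance between arms would not be tabulated.

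**Working it through.** **Inputs from the documents.** Placebo rate r0 = 0.5 per 24 weeks and n = 220 per arm (SAP 6.2); rate ratio RR = 0.60 or 0.67 (reductions of 40% and 33%, SAP 6.2); 1:1 allocation (SAP 6.3); test at the 0.05 level (SAP 8.3.2.2.2), taken as two-sided.

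**Inputs not in the documents.** The dispersion k, and the share f of k that the history would explain. Both are assumed below and shown as a range.

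**Formula.** Wald test on the log rate ratio, with r1 = 0.5 × RR:

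- Var(log RR) = [1/r0 + 1/r1 + 2k] / n
- Power = Φ(|ln RR| / SE − 1.96)

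**Step 1: the plan's own figures.** SAP 6.2 states "the power to detect a 40% reduction in the pulmonary exacerbation rate in the active arm versus the placebo arm is about 92" percent and "The power to detect a 33% reduction in the pulmonary exacerbation rate is about 78" percent, and adds: "This power calculation is based on an R simulation with 10,000 replications". The dispersion, the test and the covariates used in that simulation are not given. At k = 0:

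- 40% reduction: Wald 90.7%; null-variance form 91.7%; 10,000 simulated Poisson trials 91.5% to 91.7%. Stated: 92%.
- 33% reduction: Wald 75.8% (76.7% if RR is read as 2/3); null-variance form 77.0% to 77.9%; simulation 76.5% to 76.8%. Stated: 78%.

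With a negative binomial test and positive dispersion, the formula moves away from the stated figures. For the 40% reduction, k = 0.25, 0.5 and 1 give 88.0%, 85.3% and 79.9% (simulated: 88.5%, 85.1% and 80.6%). The stated power therefore matches a calculation with dispersion at or near zero.

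**Step 2: one worked case.** For RR = 0.67, 1/r0 + 1/r1 = 2 + 1/0.335 = 4.985, and |ln 0.67| = 0.4005.

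- k = 1: SE = √(6.985/220) = 0.1782; 0.4005/0.1782 − 1.96 = 0.288; power 61.3%.
- k = 0.7 (30% explained): SE = √(6.385/220) = 0.1704; 0.4005/0.1704 − 1.96 = 0.391; power 65.2%.
- Variance ratio: 6.985/6.385 = 1.094, equivalent to about 9% more subjects.

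**Step 3: the range for a 33% reduction.** The covariate turns k into k(1 − f).

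| Assumed k | Without history | f = 10% | f = 40% | Gain, points |
|---|---|---|---|---|
| 0 | 75.8% | 75.8% | 75.8% | 0 |
| 0.25 | 71.8% | 72.2% | 73.4% | 0.4 to 1.6 |
| 0.5 | 68.0% | 68.7% | 71.0% | 0.7 to 3.0 |
| 1 | 61.3% | 62.6% | 66.6% | 1.3 to 5.3 |
| 1.5 | 55.7% | 57.3% | 62.6% | 1.6 to 6.9 |

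For the 40% reduction at k = 1 with 30% explained, power goes from 79.9% to 83.1%.

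**The case against.** The strongest objection is that the gain is not shown to exist. It needs overdispersion left over after sex, age group and ppFEV1, and a history variable that predicts beyond them. The documents give no figure for either, and the stated power fits best at near-zero k, where the covariate gains nothing. This stands, and it is why the range starts at nil. It does not dispose of the point. The power figures rest on planning assumptions, not on trial data. By making negative binomial the main model and Poisson only the fallback, the plan itself allows for overdispersion. If k is near zero, the added term costs little.

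The variable is also imperfect. The endpoint counts new or changed IV, inhaled or oral antibiotics for four or more signs or symptoms, so outpatient courses count. The listed history is not restricted to pulmonary causes and is not a count of protocol-defined exacerbations. A reader might take it as a direct measure of the tendency to exacerbate; the documents support only a proxy. The case report form is not available, so how complete and codable the entries are cannot be seen.

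Finally, the model already covers all three stratification factors, with ppFEV1 as a continuous term, and randomization protects validity. This too stands: nothing in the plan is contradictory or biased here. Parts of the SAP's efficacy section are redacted and could contain supportive exacerbation analyses, so only the main model can be judged.

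**Conclusion.** This holds as an optional improvement. Precision may be lost at step 3 because a baseline variable already held is left out of the model. The possible gain for a 33% reduction is nil to about 7 power points, for k from 0 to 1.5 and 10% to 40% of it explained. Both ranges are assumptions. The result also relies on the Wald approximation at 220 per arm.

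Three stronger readings are not supported:

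- That precision is lost as a matter of fact. Neither the dispersion nor the prognostic strength of the history is documented.
- That the omission is an error or biases the rate ratio. Under randomization and a log link it does neither.
- That the same argument extends to the time-to-first-exacerbation Cox model. There, adding a covariate can change the hazard ratio being estimated, so the unchanged-estimand argument does not carry over.

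**What to change.** Before unblinding, add one sentence to SAP 8.3.2.2.1 that puts the number of past-year hospitalizations (0, 1, 2 or more, with a missing category) into the negative binomial model alongside the planned covariates. Carry it into the Poisson fallback, which is to use the same covariates. Add the variable to the baseline summaries by arm in SAP 8.2.2. Leave the Cox model as planned.

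The cost is one derived variable, coding of the history entries before database lock, and a few degrees of freedom. SAP Section 3 says the SAP is finalized before lock and prevails over the protocol on methods, so the change can be made there. The downside is that an all-cause proxy may add little, and adds little or nothing if overdispersion turns out to be small.
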